Data analysis plan

Mediators of treatment efficacy in "Exposure-based Cognitive Behavior Therapy vs Traditional Cognitive Behavior Therapy for Fibromyalgia" (NCT05058911)

This plan was completed on 11 May 2023 and describes a secondary study of mediators of treatment efficacy in a randomized controlled trial of Internet-delivered exposure-based cognitive behavior therapy (Exp-CBT) versus Internet-delivered traditional cognitive behavior therapy (T-CBT) for fibromyalgia.

Variables of interest

Variables of interest were administered before treatment, each week during treatment, and after treatment, resulting in 11 measurement points over the main phase of the trial.

Outcome

Fibromyalgia severity (Fibromyalgia Impact Questionnaire; FIQ)

Potential mediators

Avoidance behavior (Psychological Inflexibility in Pain Scale – Avoidance subscale; PIPS-A)
 Catastrophizing (Pain Catastrophizing Scale; PCS)
 Hypervigilance (Pain Vigilance and Awareness Questionnaire; PVAQ)
 Overdoing (Patterns of Activity Measure – Pain – Overdoing subscale; POAM-O)
 Pacing (Patterns of Activity Measure – Pain – Pacing subscale; POAM-P)
 Physical activity (Godin-Shephard Leisure-Time Exercise Questionnaire; GLEQ)

Theoretical framework: hypothesized relationships

Hypotheses with regard to mediation are listed in Table 1. All potential mediators will also be evaluated with regard to temporal precedence, i.e., whether change in the potential mediator systematically precedes change in the outcome. In all cases where the main test of mediation is not exploratory, we expect change in the potential mediator to systematically forego change in the outcome. Notably, however, because measurements were conducted on a weekly basis, the test of temporal precedence will pertain to week-by-week time-lagged effects only. This means that, potentially, temporal relations of higher resolution (e.g., day-by-day, hour-by-hour) that could explain mediation cannot be detected using this study design. Against this background, in this study, we do not regard a significant result from the test of temporal precedence to be a prerequisite for mediation.

Table 1. Overview of hypothesized mediators

Potential mediator	Hypothesis for Exp-CBT	Hypothesis for T-CBT
Avoidance behavior ^a	Yes, a reduction in the mediator is positively associated with reduction in fibromyalgia severity	Yes, a reduction in the mediator is positively associated with reduction in fibromyalgia severity
Catastrophizing	Yes, a reduction in the mediator is positively	Yes, a reduction in the mediator is positively

	associated with reduction in fibromyalgia severity	associated with reduction in fibromyalgia severity
Hypervigilance	Yes, a reduction in the mediator is positively associated with reduction in fibromyalgia severity	Exploratory only
Overdoing	Exploratory only	Yes, a reduction in the mediator is positively associated with reduction in fibromyalgia severity
Pacing	Exploratory only	Yes, an increase in the mediator is positively associated with reduction in fibromyalgia severity
Physical activity ^b	Yes, an increase in the mediator is positively associated with reduction in fibromyalgia severity	Yes, an increase in the mediator is positively associated with reduction in fibromyalgia severity

Exp-CBT: exposure-based cognitive behavior therapy; T-CBT: traditional cognitive behavior therapy.

^a Because functional impairment is measured as part of the FIQ, and these items (1-11) could be argued to overlap with avoidance, a sensitivity analysis will be conducted using only those items of the FIQ that do not measure functional impairment.

^b Will also be included in a multivariate model together with avoidance behavior, to control for the potential confounder that a mediating effect decreased avoidance can be explained by of increased physical activity.

Analytical framework

Initial inspection of variables

Baseline distributions, correlations, and development over time will be visually inspected with regard to all variables of interest.

Main mediation analysis

Because, in terms of mechanisms, we are primarily interested in the processes of Exp-CBT and T-CBT per se, as opposed to significant differences in processes between the treatments, the main analyses will be conducted within each group separately, i.e., the mediation analyses are strictly within-group analyses. For each treatment, we will test for mediation in a parallel process growth curve modelling framework. First, unconditional growth in the putative mediator and the outcome will be modelled separately, each with a random intercept and a random slope. Second, the role of the putative mediator as a predictor (not mediator) of change in the outcome will be tested by entering both variables in the same model and regressing the slope of the outcome on the random intercept of the putative mediator. Third, we will test for mediation based on bootstrapping. This is a test of the slope of the mediator (equivalent to the a-path, should time be conceptualized as independent variable of a traditional mediation model) multiplied by the effect of the mediator slope on the outcome slope (equivalent to the b-path, should time be conceptualized as the independent variable of a traditional mediation model).

Conditional indirect effects

Fourth, we will evaluate if the general level on the potential mediator (e.g., the general level of avoidance) is a moderator of mediation via the same variable (e.g., mediation via avoidance). In this step, we will test the indirect path from the random intercept of the potential mediator, to the slope of the potential mediator, to the slope in the outcome. This is not a test of moderation of the b-path (see above; [1]). Therefore, fifth, a moderating effect on the b-path will also be tested in a linear mixed model framework, where the outcome is regressed on the time-lagged potential mediator, the baseline value of the mediator, time, and all interactions. This will be a test of the baseline mediator \times time-lagged mediator coefficient.

Week-by-week temporal ordering: random-intercepts cross-lagged panel models

The above analyses do not test whether change in the potential mediator systematically precedes change in the outcome. Therefore, for each treatment, we will test for temporal precedence using random-intercepts cross-lagged panel models.

Sensitivity analyses

As is specified above, two sensitivity analyses of the main test of mediation will be conducted with regard to avoidance behaviors. First, the analysis will be repeated without the use of functional impact items of the FIQ (item 1-11). Second, a multivariate model that includes physical activity will be fit to determine whether avoidance behavior has a specific effect beyond physical activity.

Secondary analyses

Pain intensity as a potential moderator of processes of change

In a previous trial, we found that the Brief Pain Inventory – Short form, severity subscale (BPI-SF) was a moderator of the effect of Exp-CBT versus a waitlist control. Though, in this trial, the BPI-SF was not a moderator of the between-group effect of Exp-CBT versus T-CBT, we intend to explore if BPI-SF is a moderator of the processes of change in Exp-CBT and T-CBT respectively. Therefore, the baseline BPI-SF value will be evaluated in a manner analogous to the intercept of the mediator in steps four and five above.

Count variables pertaining to treatment engagement in relation to the outcome

Three measures of treatment engagement were developed as count variables for this trial. In Exp-CBT, the number of conducted exposure exercises and mindfulness exercises were reported by the participants. In T-CBT, participants reported the number of conducted relaxation exercises. All were reported on a weekly basis. Overall correlations will be calculated between the total number of each respective treatment activity and the outcome (FIQ). Because we expect data to be non-normally distributed, Spearman correlations will be used. If model convergence can be achieved, these count variables will also be analyzed in cross-lagged panel models.

The item used for capturing work with exposure reads “*How many exposure exercises have you conducted during the last 7 days? If unsure, please try to estimate to the best of your ability*”. Engagement with mindfulness exercises will be quantified by summarizing the responses on the following items: “*How many times have you conducted the exercise ‘mindfulness through focus on breathing, the body and the surrounding environment’, during the last 7 days? If unsure, please try to estimate to the best of your ability*”; “*How many times*

have you conducted the exercise ‘everyday mindfulness’, during the last 7 days? If unsure, please try to estimate to the best of your ability”; and “How many times have you conducted the exercise ‘mindfulness when experiencing symptoms’, during the last 7 days? If unsure, please try to estimate to the best of your ability”. The item for capturing work with relaxation exercises reads “How many times have you practiced relaxation during the last 7 days? If unsure, please try to estimate to the best of your ability”.

Avoidance as a potential mediator on catastrophizing and hypervigilance

In Exp-CBT, avoidance behavior will also be tested as a potential mediator of the effect on catastrophizing and hypervigilance.

References

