given an FM diagnosis and subsequently complete a series of self-report screening questionnaires including routine questions concerning sociodemographic characteristics, FM, medical status, and symptoms. Complete applications are reviewed and followed by a structured telephone interview to inform about the study, collect key clinical data, and assess the study eligibility criteria. Applicants who meet all eligibility criteria are informed that they will be included and randomized after they have completed the pre-treatment assessment. The eligibility interview is conducted by a licenced psychologist, resident psychologist, or psychologist- or psychotherapist student under supervision of a licensed psychologist with knowledge of FM and common psychiatric comorbidities. Individuals who are excluded are informed about the reason for this, and referred to routine care services as necessary.

Randomization

Randomization is conducted 1:1 using the www.random.org service, on a cohort-by-cohort basis, by an external person who is blind to participant characteristics.

Table 1. *Measurements*

Questionnaire	Outcome	Reference	SN	PRE	WK	POST	6M FU	12M FU
Efficacy outcomes								
FIQ	Composite FM severity	(Burckhardt et al., 1991)	x	x	x	x	x	x
FIQ subscale	Pain, primary measure		x	x	x	x	x	x
FSS	Fatigue	(Krupp et al., 1989)		x		x	x	x
BPI-S	Pain, secondary measure	(Mendoza et al., 2006)		x		x		
GAD-2*	Anxiety	(Kroenke et al., 2007)		x		x	x	x
PHQ-2*	Depression (outcome)	(Kroenke et al., 2003)		x		x	x	x
WHODAS 2	Functional impairment	(Üstün et al., 2010)		x		x	x	x
BBQ	Quality of life	(Lindner et al., 2016)		x		x	x	x
PGIC	Impression of change	(Hurst & Bolton, 2004)				x		
Screening only								
MADRS-S	Depression (screening)	(Svanborg & Asberg, 1994)	x	a	a	a	a	a
AUDIT	Alcohol use	(Saunders, Aasland, Babor, de la Fuente, & Grant, 1993)	x					
DUDIT	Drug use	(Berman, Bergman, Palmstierna, & Schlyter, 2005)	x					
Primarily used to investigate processes								
PIPS-avoid	Avoidance	(Wicksell et al., 2010)		x	x	x	x	x

Exposure-based CBT vs. traditional CBT for patients with fibromyalgia
Study protocol intended for expert review

POAM-P-p/o	Pacing and overdoing	(Cane et al., 2013)		x	x	x	x	x
PCS	Catastrophizing	(Sullivan et al., 1995)		x	x	x	x	x
PVAQ	Hypervigilance	(Roelofs et al., 2003)		x	x	x	x	x
C/E	Credibility, expectancy	(Deville & Borkovec, 2000)			w. 2			
WAI-S	Therapeutic alliance	(Hatcher & Gillasp, 2006)			w. 2			
GSLTPAQ	Physical activity	(Godin, 2011)		x	x	x		

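### The within-arm mediation test is never adjusted for baseline FIQ, so baseline severity that drives change on both scales could be reported as mediation

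*SAP*

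**What the plan says.** The SAP (Main mediation analysis; Conditional indirect effects) sets out five steps, all within arm.

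- **Step one** models mediator and FIQ growth separately, "each with a random intercept and a random slope".
- **Step two** tests the mediator as a predictor by "regressing the slope of the outcome on the random intercept of the putative mediator".
- **Step three** is the mediation test: the mediator slope "multiplied by the effect of the mediator slope on the outcome slope", with bootstrapping. It names no covariate and does not say whether the step-two term is kept.
- **Step four** asks whether "the general level on the potential mediator" moderates mediation, through the path from mediator intercept to mediator slope to FIQ slope.
- **Step five** is a mixed model in which "the outcome is regressed on the time-lagged potential mediator, the baseline value of the mediator, time, and all interactions".

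Table 1 note b adds physical activity to the avoidance model "to control for the potential confounder that a mediating effect decreased avoidance can be explained by of increased physical activity". The other sensitivity analysis drops FIQ items 1-11. For baseline pain, a secondary analysis says that "the baseline BPI-SF value will be evaluated in a manner analogous to the intercept of the mediator in steps four and five above".

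Temporal order is tested separately with random-intercepts cross-lagged panel models. The SAP states that the growth models do not test order, and that a significant lag is not required for mediation because faster-than-weekly effects would be missed.

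**The concern.** The b-path is a regression of one person-level slope on another within a single treatment arm. Randomisation balances baseline severity between arms but does nothing for this regression; only covariates can protect it. The plan accepts that logic when it adjusts avoidance for physical activity, yet it never adjusts for the baseline level of the outcome itself.

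If patients with worse baseline FIQ change more on both scales, the two slopes correlate even when the mediator has no effect on FIQ. The concern is plausible on the plan's own account: baseline pain severity moderated the effect of Exp-CBT against a waitlist in an earlier trial, and FIQ contains a pain subscale. That does not give the correlation, and the SAP adds that pain did not moderate the between-group effect in this trial.

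Step three is the main test in every cell of Table 1: 6 mediators × 2 arms = 12 cells, of which 3 are exploratory and 9 carry a hypothesis.

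**Working it through.** **Inputs from the documents.** 130 per arm and 10% missing at each post-baseline point (protocol, Design); 11 measurement points (SAP, Variables of interest); the five steps above. The plan states no figure on this point, so there is none to reproduce.

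**Assumed inputs.** Intercept-slope correlations and variance components are not given. Let g be the correlation of baseline FIQ with each slope, and r = 0.5 the correlation between the two baselines. All variances are 1 and the true b is 0.

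**1. False b in closed form, linear change.** The two slopes share only baseline FIQ, so their covariance is g × g.

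- No adjustment: b = g².
- Mediator intercept only (its correlation with each slope is g·r): b = (g² − (g·r)²) / (1 − (g·r)²).
- FIQ intercept added: b = 0.

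For g = -0.3: 0.090; (0.090 − 0.0225)/(1 − 0.0225) = 0.069; 0.
For g = -0.4: 0.160; (0.160 − 0.040)/0.960 = 0.125; 0.
For g = -0.5: 0.250; (0.250 − 0.0625)/0.9375 = 0.200; 0.

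**2. False mediation rate (bootstrap interval for a × b excludes zero).** Simulation 1: 2000 runs, slope reliability 0.65, mean mediator slope -0.6 SD, 10% missing, 400 resamples. Simulation 2: 400 runs, residual variance 0.5, mean mediator slope -0.7 SD, complete data, 300 resamples. Each cell shows unadjusted / mediator intercept only / both intercepts at pre-treatment.

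| g | Simulation 1 | Simulation 2 |
|---|---|---|
| 0 | 6% / 6% / 6% | 7% / 6% / 7% |
| -0.2 | 7% / 7% / 6% | 10% / 10% / 8% |
| -0.3 | 11% / 9% / 6% | 17% / 14% / 8% |
| -0.4 | 22% / 17% / 6% | 32% / 24% / 8% |
| -0.5 | 45% / 32% / 6% | 55% / 42% / 8% |

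The pattern agrees. The level depends on the assumed variances.

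**3. Other structures.** If each slope follows its own baseline, b unadjusted is g·r·g: 0.045 at g = -0.3 and 0.125 at -0.5. With the mediator intercept in the model it is 0. Simulated false mediation (400 runs) is then 10% and 17% unadjusted, and 5% and 7% with the mediator intercept. If baseline FIQ correlates -0.2 with the mediator slope and -0.5 with the FIQ slope, b = 0.2 × 0.5 = 0.10 and the rate is 14%. So the mediator intercept alone is enough only when baseline FIQ does not itself drive the mediator slope.

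**4. Time zero.** Shifting time zero leaves the slopes and their covariance unchanged, so step three as written is unaffected. It matters once intercepts are adjusters. With both intercepts coded at mid-treatment, Simulation 1 gives false mediation of 14% at g = 0, 41% at -0.3 and 66% at -0.5, because a mid-treatment intercept already contains part of the slope.

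**5. Growth shape.** Suppose change follows (1 − e^(−kt))/(1 − e^(−k)) over t = 0 to 1 in 11 equal steps. With k = 2, 73% of change has occurred by half-time; with k = 4, 88%. A least-squares line then has a time-zero value of 0.163 or 0.311 of total change, so the fitted intercept absorbs change. At g = -0.3, b with both intercepts is 0.069 (k = 2) or 0.160 (k = 4), against 0.090 unadjusted. The linear adjustment helps little in the first case and does harm in the second.

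**6. Cost in power (Simulation 1, true b = 0.3).** At g = 0, power is 59% unadjusted and 56% with both intercepts. At g = -0.3 it is 80% and 62%, but the 80% rests on an inflated median b of 0.39, against 0.31 adjusted.

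**The case against.** **The growth model already lets intercepts and slopes covary.** This does not help. A covariance between FIQ intercept and FIQ slope does not adjust the regression of one slope on another; the intercept has to be a predictor.

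**The size is speculative.** This stands. No document supports a correlation of -0.4 or beyond, the effect is negligible near -0.2, and the equal-drive structure is unfavourable to the plan.

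**The adjustment can itself fail.** This also stands. It works only with time zero at pre-treatment and a growth shape that fits, so the adjusted result belongs beside the planned one rather than in its place.

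**A reader might infer that the unstated time origin undermines the main test.** It does not, because step three is invariant to time zero. The SAP also pairs the intercept of step four with the baseline value of step five when it describes the BPI-SF analysis. That points towards pre-treatment, although the "general level" wording of step four leaves it unstated.

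**A reader might also infer that a lag running only from FIQ to mediator should disqualify the mediator.** In one set of simulations where only FIQ drove the mediator (weekly lag 0.15 / 0.30), a × b was significant with a reverse-only lag in 89% / 96% of runs, so the pattern deserves to be seen. But a reverse-only result includes a null forward lag, and the SAP openly says that a significant lag is not a prerequisite. The protocol's background also describes avoidance and pain impact as feeding each other. With true within-week mediation (0.3) plus weekly FIQ feedback (0.15), a simplified lagged regression gave reverse-only in 12%, 67% and 83% of runs at autoregression 0.3, 0.15 and 0.1. A relabelling rule would therefore reject true mediators and override a disclosed choice.

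**Conclusion.** The gap is real. No step or sensitivity analysis adjusts the b-path for baseline FIQ, and within an arm nothing else protects it from baseline severity. Under linear change with baseline FIQ driving both slopes equally, false mediation is close to nominal at a correlation of about -0.2 and large from about -0.4 (22% to 32% across the two simulations). It is smaller under the other structures examined. Every rate rests on assumed correlations and variances; the direction of the bias does not depend on them, provided baseline FIQ moves both slopes the same way.

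The documents do not support saying that the mediation results will be false, that time coding invalidates step three, or that a reverse lag must remove the mediation label. This is a worthwhile, inexpensive strengthening of a secondary study. The primary efficacy test, the time-by-group coefficient, is unaffected.

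**What to change.** 1. For each mediator and arm, report step three twice: as planned, and with the FIQ slope also regressed on the mediator and FIQ intercepts, with time zero stated as pre-treatment.
2. Choose the growth shape from the visual inspection of development over time that the SAP already plans, for example freely estimated time loadings if change is front-loaded.
3. Report the FIQ intercept-slope correlation, so readers can judge how much the adjustment could matter.
4. Describe a mediator as robust to baseline severity only if the indirect effect holds in both versions.
5. Report both cross-lagged directions, and say plainly when only FIQ-to-mediator is supported, without making that a rule on the mediation label.

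No new data are needed: applicants are told that "they will be included and randomized after they have completed the pre-treatment assessment", and the protocol's measurement table includes FIQ at that assessment. The cost is SAP wording, two regression terms per model, power falling from about 59% to 56% when baseline FIQ does not drive the slopes (more when it does, partly by removing inflation), and possible convergence problems with missing waves or free loadings.

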STUDY PROTOCOL

RANDOMIZED CONTROLLED TRIAL OF INTERNET-DELIVERED EXPOSURE-BASED COGNITIVE BEHAVIOR THERAPY VS. INTERNET- DELIVERED TRADITIONAL COGNITIVE BEHAVIOR THERAPY FOR PATIENTS WITH FIBROMYALGIA

Document date: 2021-06-11

Study protocol

Randomized controlled trial of internet-delivered exposure-based cognitive behavior therapy vs. internet-delivered traditional cognitive behavior therapy for patients with fibromyalgia

Summary

Fibromyalgia (FM) is a common medical condition characterized by chronic generalized musculoskeletal pain, fatigue, and a series of additional somatic and psychiatric problems that give rise to distress, functional impairment, and substantial societal costs. The most extensively evaluated treatment for FM is traditional cognitive behavior therapy (T-CBT) which typically appears to have small to moderate effects when compared to waitlist, attention control, treatment as usual or other active nonpharmacological therapies. Internet-delivered exposure-based cognitive behavior therapy (Exp-CBT) where the patient willingly and systematically engages with stimuli associated with pain and pain-related distress has shown promising controlled effects versus a waiting-list but has never been compared to T-CBT in a randomized controlled trial. In this randomized controlled trial, self-recruited adults with FM (N=260) are randomly assigned (1:1) to 10 weeks of internet-delivered Exp-CBT or internet-delivered T-CBT and complete self-report questionnaires to measure symptoms and therapeutic processes up to 12 months after treatment. Primary outcome is the relative effect of Exp-CBT and T-CBT on FM severity as modelled using linear mixed models fitted on weekly Fibromyalgia Impact Questionnaire sum scores over the treatment period, testing the hypothesis of Exp-CBT superiority based on the coefficient for the time \times group interaction. Cost-effectiveness and mediational processes are investigated in secondary analyses. We expect this trial to be of notable clinical significance as it will provide valuable information about the value of Exp-CBT in helping patients with FM as compared to using other interventions.

Overview of the field

Fibromyalgia: a common, disabling, and costly chronic pain condition

Fibromyalgia (FM) is a chronic pain syndrome affecting approximately 2-4% of the general population, and most typically (90%) women (Queiroz, 2013). The condition is characterized by chronic musculoskeletal pain, stiffness, fatigability, and decreased pain threshold (Smith, Harris, & Clauw, 2011). Diagnostic criteria for FM according to the American College of Rheumatology are the following: 1) generalized pain defined as pain in at least four out of five regions (left and right upper region, left and right lower region; axial region), 2) the symptoms have persisted for at least 3 months, and 3) either at least 7 points on the Widespread Pain Index (WPI) and at least 5 points on the Symptom Severity Scale (SSS) *or* at least 4 points on the WPI and at least 9 points on the SSS (Wolfe et al., 2011). Individuals with FM also commonly experience other somatic and psychiatric symptoms such as disturbed sleep, tension headache, migraine, fatigue, gastrointestinal problems, cognitive impairment, dizziness, low mood, anxiety, and increased sensitivity to stress (Wolfe, Ross, Anderson, Russell, & Hebert, 1995). The condition is associated with functional impairment, substantially lowered quality of life (Hauser et al., 2015), and also notable societal costs due to its effects on health care expenditure, sick leave, and work status (Rivera, Rejas, Esteve-Vives, Vallejo, & ICAF, 2009).

The avoidance of pain is predictive of poor health outcomes

The experience of pain relies on a complex interaction of biological, psychological, and social factors (Gatchel, Peng, Peters, Fuchs, & Turk, 2007). A number of psychological factors have been found to be especially important, including attentional, emotional, and cognitive processes. An important factor in the maintenance of pain over time is pain-related avoidance, i.e., that the patient starts avoiding situations and activities where pain might occur, whereby the avoided

situations and activities by classical and operant conditioning become associated with pain and pain-related distress. Pain-related avoidance often implies a reduction in meaningful activities such as social interaction and work, and often leads to a vicious cycle where a shrinking behavioral repertoire feeds the impact of pain on everyday life, which leads to more avoidance, more attention devoted to pain instead of meaningful activities, and so on (Wicksell et al, 2008). Numerous studies have indicated that pain-related avoidance is predictive of increased pain, increase attention to pain, and increased functional impairment (Geisser, Haig, & Theisen, 2000; Goubert, Crombez, Eccleston, & Devulder, 2004; McCracken, Eccleston, & Bell, 2005; Philips & Jahanshahi, 1985; Prkachin, Schultz, & Hughes, 2007).

Importance of psychological treatment

While pharmacological treatment for FM with antidepressants and anticonvulsants (Arnold, 2006; Goldenberg, Burck, Hardt, Crofford, 2004) can reduce pain and other FM-related symptoms, of those who receive pharmacological treatment for FM, only about 40% experience clinically significant improvement (Arnold, 2006) and the utility of pharmacological treatment has been therefore questioned (Nüesch, Hauser, Bernardy, Barth, & Jüni, 2013). Non-pharmacological treatments are commonly at least as efficacious (Rossy et al., 1999).

Traditional cognitive behavior therapy

Traditional cognitive behavior therapy (T-CBT) is the most widely evaluated psychological treatment for FM with over 40 randomized controlled trials. In the majority of these trials, T-CBT protocols have been composite interventions, based on a combination of treatment components such as relaxation, problem solving, psychoeducation, stress management practices, and cognitive restructuring techniques. A widely used treatment component with relatively robust support has been *pacing*: the systematic dosing of activity level to achieve energy conservation. The patient is encouraged to use particular strategies before, during, and after activities in order to moderate pain (Hammond, 2004).

Bernardy and colleagues published a 2013 systematic Cochrane review and meta-analysis of randomized controlled trials of cognitive-behavioral interventions (including acceptance and commitment therapy) for FM (Bernardy, Klose, Busch, Choy, & Hauser, 2013). Their conclusion was that such treatments give a small but significant added effect on pain, mood, and functional impairment as compared to waitlist control, attention control, treatment as usual or other nonpharmacological therapies. An update was published in 2017 including trials conducted between 2013-2017 (Bernardy, Klose, Welsch, & Hauser, 2017). In this review, CBT was found to provide a clinical benefit over control interventions in reducing some core symptoms and disability at the end of treatment, but did not change the major findings from the original review.

Exposure-based cognitive behavior therapy

Exposure is among the most widely employed treatment components in psychological treatments for common anxiety disorders (Koran et al., 2007; National Collaborating Centre for Mental Health, 2005, 2006, 2011, 2013; Ursano et al., 2004) and has also been evaluated with promising results for several somatic conditions (Bonnert et al., 2016; Craske et al., 2011; Ljótsson, Hedman, et al., 2011). Exposure therapy is based on repeated and maintained confrontation with stimuli that give rise to unwanted responses, and is conducted with the aim of achieving therapeutic effects, usually conceptualized as some sort of new learning. Exposure for somatic conditions implies that the patient systematically engages in exposure exercises, such as by provoking discomfort or feared symptoms, approaching avoided activities and situations in a new manner without resorting to distraction. Exposure also implies refraining

Exposure-based CBT vs. traditional CBT for patients with fibromyalgia Study protocol intended for expert review

from so called safety- and avoidance behaviors intended to reduce unwanted emotions or discomfort in the short term. The mechanism of action by which exposure works is not fully understood, but it is commonly hypothesized that repeated exposure leads to an increased tolerance of unwanted emotions or discomfort, and that the patient gradually develops a stronger belief in his or her ability to manage symptoms and situations previously feared or avoided (Tryon, 2005).

Considering that avoidance behavior contributes to maintain pain over time, exposure has been suggested as a key intervention for patients suffering from chronic pain, and has also been evaluated for chronic pain conditions in a few randomized controlled trials (den Hollander et al., 2016; Leeuw et al., 2008; Linton et al., 2008; Woods & Asmundson, 2008). Our research group has previously developed and evaluated exposure-based treatment for patients with FM in a pilot study and subsequent large-scale RCT (Hedman-Lagerlöf et al., 2018; [name] et al., 2014), both with promising results as detailed below. Considering that pain-related avoidance behavior exists in many forms including covert processes such as distraction, resisting, and checking, exposure treatment can be tailored to a wide spectrum of individuals with fibromyalgia including those who do not exhibit avoidance that is visible to the eye

Delivering psychological treatment via the internet

Treating patients with psychological methods via the internet has become increasingly common in recent years (Andersson, 2009). Use of the internet to deliver interventions has several advantages, including high cost-effectiveness since the intervention commonly demands less time from the therapist and can be more easily distributed compared to face-to-face treatment. A systematic review by Carlbring and colleagues (2018), demonstrates that therapist-guided treatment often results in effects similar to those of conventional face-to-face treatment. Internet-delivered T-CBT for FM has been evaluated in two RCTs with mixed results (Friesen et al., 2017; Vallejo, Ortega, Rivera, Comeche, & Vallejo-Slocker, 2015).

Our research group has evaluated exposure-based cognitive behavior therapy (Exp-CBT) for FM in two clinical trials. First, in 2012, we completed a pilot trial (regional ethics review board of Stockholm identifier 2011/1499-31/4) where 41 participants with FM took part in a 10-week internet-delivered psychological treatment program that emphasized systematic exposure. Results were indicative of substantial change from pre- to post-treatment ($p < 0.001$) in all outcome domains, with moderate to large standardized effects ($d = 0.65-1.21$) ([name] et al., 2014). In the subsequent RCT, 140 participants were randomized to 10 weeks of Exp-CBT or a waiting-list, resulting in large waitlist-controlled effects on FM-symptoms, pain, fatigue, functional impairment and pain-related anxiety. The study also indicated that Exp-CBT, compared to no treatment, is highly cost-effective, and that a reduction in FM-related avoidance was associated with a larger treatment effect. A clear limitation in the current body of knowledge, however, is that exposure-based treatment for FM has not been compared to an active control group. Our knowledge of treatment moderators and mechanisms is also limited.

Summary of background

In conclusion, FM is a common problem with substantial negative consequences. The most widely evaluated psychological treatment for FM is T-CBT which usually has small to moderate controlled effects on pain, mood and functional impairment. Based on one pilot study and one waitlist-controlled RCT, Exp-CBT appears to have promising effects on FM but this treatment has not yet been compared to an active control condition. The present study aims to compare internet-delivered Exp-CBT to internet-delivered T-CBT in a randomized controlled trial. In addition to clinical efficacy, we will also investigate cost-effectiveness and mediational

Exposure-based CBT vs. traditional CBT for patients with fibromyalgia
Study protocol intended for expert review

processes. Primary hypothesis is that Exp-CBT will be more efficacious than T-CBT in reducing FM severity, i.e., a composite score indicative of symptoms and functional status, as assessed using the primary outcome Fibromyalgia Impact Questionnaire (FIQ).

Overarching aim of the study

The overarching aim of the study is to evaluate the clinical efficacy of internet-delivered exposure-based cognitive behavior therapy (Exp-CBT) compared to internet-delivered traditional cognitive behavior therapy (T-CBT) for patients with fibromyalgia (FM) in a large-scale randomized controlled trial.

Primary research question

Does Exp-CBT, compared to T-CBT, produce a larger reduction in FM severity over the 10-week treatment period? Hypothesis: Yes.

Secondary research questions

- 1) Does Exp-CBT, as compared to T-CBT, produce larger controlled effects on A) pain, B) fatigue, C) quality of life, D) functional impairment, E) depression, and F) anxiety? Exploratory.
- 2) Is Exp-CBT more cost-effective than T-CBT? Hypothesis: Yes.
- 3) What factors moderate the treatment outcome? Hypotheses will be fully formulated and registered prior to the analysis, when the precise modeling approach has been chosen.
- 4) What factors mediate the treatment outcome? Hypotheses will be fully formulated and registered prior to the analysis, when the precise modeling approach has been chosen.

Methods

Design

This is a randomized controlled trial with repeated measurements and two conditions: the experimental group (Exp-CBT) and an active control group (T-CBT). Based on previous trials, we expect an Exp-CBT within-group effect of approximately 16.9 points (Hedman-Lagerlöf et al., 2018) and a corresponding T-CBT within-group effect of no more than 9 points (Castel, Salvat, Sala, & Rull, 2009; King, Wessel, Bhambhani, Sholter, & Maksymowych, 2002; Redondo et al., 2004) on the Fibromyalgia Impact Questionnaire (Burckhardt, Clark, & Bennett, 1991). Given this scenario, Monte Carlo simulation ($n=1000$) of multi-level linear regression analyses with 11 weekly measurements and an expected data loss of 10% at every measurement point after baseline indicated that 130 participants will be needed per arm (Exp-CBT vs. T-CBT) for 80% power in testing the time \times group coefficient ($\alpha=.05$).

Eligibility criteria

The study will be open for adults of at least 18 years diagnosed with FM living in Sweden, with access to the internet and with a completed pre-treatment assessment. Concurrent psychotropic medication is allowed if the dose has been stable for at least 4 weeks before randomization and the participant agrees to keep it constant during treatment. Exclusion criteria are the following: A) severe depression (≥ 30 on the Montgomery Åsberg Depression Rating Scale—Self Rated [MADRS-S] at screening), B) suicidal ideation (≥ 4 on the suicide item of the MADRS-S at screening), C) psychosis, D) alcohol or substance use disorder as primary diagnosis or likely to severely interfere with treatment, E) ongoing psychological treatment, F) pregnancy (>29 wk gestation), G) another somatic condition that requires immediate treatment and/or is deemed to be the primary condition, and H) insufficient knowledge of the Swedish language or insufficient computer skills to benefit from the text-based online treatment.

Outcome measures

- **Composite FM severity: symptoms and functional status (primary outcome).** The Fibromyalgia Impact Questionnaire, FIQ (Burckhardt, Clark & Bennett, 1991). This is a validated and disease-specific instrument known to be reliable and responsive to change (R. Bennett et al., 1996).
- **Pain.** The Fibromyalgia Impact Questionnaire, FIQ-Pain subscale (Burckhardt, Clark & Bennett, 1991) and Brief Pain Inventory-Short Form, BPI-S (Mendoza, Mayne, Rublee, & Cleeland, 2006)
- **Fatigue.** Fatigue Severity Scale, FSS (Krupp, LaRocca, Muir-Nash, & Steinberg, 1989).
- **Anxiety and depression.** The GAD-2 (Kroenke, Spitzer, Williams, Monahan, & Löwe, 2007) and Patient Health Questionnaire-2, PHQ-2 (Kroenke, Spitzer, & Williams, 2003)
- **Functional impairment and quality of life.** The WHO Disability Assessment Schedule 2.0, WHODAS 2 (Üstün et al., 2010), Brunnsvikens Brief Quality of Life Inventory, BBQ (Frykheden, 2014), and EQ-5D (Rabin & Charro, 2009)
- **Pain-related avoidance behavior.** The Psychological Inflexibility in Pain Scale-avoidance subscale, PIPS (Wicksell, Lekander, Sorjonen, & Olsson, 2010)
- **Pacing and overdoing behavior:** Patterns of Activity Measure – Pain: pacing and overdoing subscales, POAM-P/p/o (Cane, Nielson, McCarthy, & Mazmanian, 2013)
- **Pain-related catastrophizing.** Pain Catastrophizing Scale, PCS (Sullivan, Bishop, & Pivik, 1995)
